4.2.2 Safety Hypothesis

Primary Safety Hypothesis: VR101, when used in accordance with provided instructions for use will not result in a rate of occurrence of Serious Adverse Device Effects (SADE) greater than 1%.

P(safety) = proportion of initiated VR101 uses without a Serious Adverse Device Effect, which is equal to: Total number of initiated VR101 uses without a participant reporting a serious adverse device effect during VR101 use divided by the total number VR101 devices used.

VR101 safety will be demonstrated if the upper bound of the two-sided exact 95% confidence interval surrounding the proportion of SADE occurrence ('P(SADE)') is 0.01 or less.

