8.3 Statistical Power of Proposed Clinical Investigation to Demonstrate Device Safety

If, during the course of CI02, 30 participants use a total of 13 each VR101 devices (390 VR101 devices, total) during the long-term safety portion of the study, and an additional 30 participants use a total of 4 VR101 devices during the 4-week crossover efficacy portion (120 VR101 devices, total), then, at the conclusion of CI02, a total of 553 VR101 devices will have been used (510 total uses of VR101 devices in CI02, plus an additional 43 total VR101 devices already used in CI01 [with no SADEs observed in CI01]). Note that this total number of devices used does not account for VR101 devices used for less than 5 days whose data will not be used in assessing efficacy, but whose data will be included in the sample of devices used to assess safety. So, it is likely that the number of VR101 device uses evaluated for safety will exceed 553.

J3 Bioscience, Inc.	Clinical Investigation Plan and Protocol CI02	CI02-CIP Rev. 08 Page 54 of 75
	A Pivotal Clinical Investigation to Evaluate the Safety and Efficacy of J3 Bioscience Lubricating Intravaginal Ring VR101 in Relieving Symptoms of Vaginal Dryness	

If 2 SADEs occur out of a total 510 VR101 devices used according to instructions in the proposed investigation, then we will be able to rule out SADE rates greater than 1 event per 100 devices with 95% confidence. The 95% confidence interval for 2 events in 510 devices is (0.00, 0.01) (exact test, Minitab 17).

However, if no SADE is observed during the entirety of CI02 (0 events/510 devices), as expected, we will be able to rule out a SADE rate greater than 0.6 events per 100 devices with 95% confidence. The 95% confidence interval for 0 events in 510 observations is (0.000, 0.006) (exact test, Minitab 17).

Further, if no SADE is observed during the entirety of CI02 and CI01 (0 events/553 devices), as expected, we will be able to rule out a SADE rate greater than 0.5 events per 100 devices. The 95% confidence interval for 0 events in 553 observations is 0.000 (0.000, 0.005) (Minitab 17).

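### The zero-SADE upper limits in 8.3 (0.006 and 0.005) fit one-sided 95% bounds; the two-sided exact interval of 4.2.2 gives 0.72% and 0.66%, and pass/fail is unchanged

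*Combined protocol and SAP*

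**What the plan says.** Section 4.2.2 (Safety Hypothesis) states that VR101 "will not result in a rate of occurrence of Serious Adverse Device Effects (SADE) greater than 1"%. It also fixes the test: "VR101 safety will be demonstrated if the upper bound of the two-sided exact 95% confidence interval surrounding the proportion of SADE occurrence" "is 0.01 or less". The interval is therefore two-sided and exact, but the exact method is not named.

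Section 8.3 sets the planned number of device uses: "510 total uses of VR101 devices in CI02, plus an additional 43 total VR101 devices already used in CI01", which makes 553. It then describes the anticipated result, "if no SADE is observed during the entirety of CI02 (0 events/510 devices), as expected", and gives the limit: "The 95% confidence interval for 0 events in 510 observations is (0.000, 0.006". From this it concludes that a rate above 0.6 per 100 devices is ruled out with 95% confidence. For the two studies together it gives: "The 95% confidence interval for 0 events in 553 observations is 0.000 (0.000, 0.005", and concludes that a rate above 0.5 per 100 is ruled out.

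The 0/510 interval is described as an exact test. The 0/553 interval carries only the software name. Neither is described as one-sided.

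**The concern.** The planning section and the decision rule should use the same interval. Rounding to three decimals cannot turn a two-sided exact limit into either printed value: both two-sided limits round to 0.007. A reader who takes 8.3 at its word would expect a trial with no SADEs to exclude rates above 0.6 per 100, or 0.5 per 100 with CI01. The interval in 4.2.2 does not deliver that.

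Safety is one of the two criteria for study success in 8.5, and zero SADEs is the result the sponsor expects. These are therefore the planning figures most likely to be relied on. The choice of tail can also matter away from zero. With 1 SADE in 510 uses the one-sided limit is 0.93%, under 1%, while the two-sided limit is 1.09%, over it. That is a reason to write the convention down identically in both sections.

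**Working it through.** **Inputs.** Two-sided exact 95% interval and limit of 0.01 (4.2.2). Uses: 510 in CI02, and 510 + 43 = 553 with CI01 (8.3). Events: 0 in both cases (8.3). Printed upper limits: 0.006 and 0.005 (8.3).

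**Formula.** With 0 events in n uses, the exact (Clopper-Pearson) upper limit U solves (1 − U)^n = a, so U = 1 − a^(1/n). A one-sided 95% limit has a = 0.05. The upper end of a two-sided 95% interval has a = 0.025.

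**Reproducing the plan's figures (a = 0.05).**
- n = 510: 1 − 0.05^(1/510) = 0.00586, which rounds to 0.006.
- n = 553: 1 − 0.05^(1/553) = 0.00540, which rounds to 0.005.

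**The interval 4.2.2 calls for (a = 0.025).**
- n = 510: 1 − 0.025^(1/510) = 0.00721.
- n = 553: 1 − 0.025^(1/553) = 0.00665 (0.006648 before rounding).

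| | Printed | One-sided 95% | Two-sided 95% | Printed vs two-sided |
|---|---|---|---|---|
| 0/510 | 0.6% | 0.586% | 0.721% | 1 − 0.6/0.721 = 17% lower |
| 0/553 | 0.5% | 0.540% | 0.665% | 1 − 0.5/0.665 = 25% lower |

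Before rounding, the one-sided limit is about 19% below the two-sided one in both rows. The larger gap for 553 arises because 0.54 was rounded down to 0.5.

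**Could another two-sided method give the printed pair?** Upper limits for 510 and 553:
- Blaker: 0.0070 and 0.0064.
- Sterne: 0.0074 and 0.0068.
- Wilson: 0.0075 and 0.0069.
- Agresti-Coull: 0.0090 and 0.0083.
- Jeffreys, not exact: 0.0049 and 0.0045, which round to 0.005 and 0.005.
- Smallest limits from minimal-length exact acceptance sets: 0.00646 and 0.00596. Both round to 0.006, so the first could match but the second does not.

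None gives 0.006 together with 0.005. A two-sided mid-P limit at zero events solves 0.5(1 − U)^n = 0.025, which is the same equation as the one-sided limit, so the numbers alone cannot separate the two. Mid-P is not an exact interval, however, and 8.3 cites an exact test for 0/510.

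**Confidence behind the stated rates, taken one-sided.**
- 0.6 per 100 with 0/510: 1 − 0.994^510 = 95.4%.
- 0.5 per 100 with 0/553: 1 − 0.995^553 = 93.7%.

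**Zero-event uses needed for the printed limits to be two-sided.** ln(0.025)/ln(1 − 0.006) = 612.97, so 613. ln(0.025)/ln(1 − 0.005) = 735.9, so 736.

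**Effect on the decision.** The fewest zero-event uses with a limit of 0.01 or less is 368 two-sided and 299 one-sided. The two conventions disagree at zero events only from 299 to 367 uses, below the planned 510.

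**The case against.** The strongest defence is that 8.3 is a planning illustration. Section 8.5 ties success to 4.2.2, which says two-sided in plain words, so no decision is taken at the wrong level. This stands. It is also true that ruling out a rate above 0.6 per 100 with 95% confidence is a one-directional statement, and as such it is correct (95.4%). What does not stand is presenting the limit as a 95% confidence interval without qualification when the criterion uses a two-sided one. The defence also fails for 0.5 per 100, which falls short of 95% even one-sided.

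A second defence is that 4.2.2 says exact without naming Clopper-Pearson, and 8.4 applies that word to a Blyth-Still-Casella interval. So 0.72% and 0.66% are the Clopper-Pearson values, not the only possible exact ones. This stands as a qualification and is a reason to name the method.

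Three stronger readings are tempting, but the documents do not support them:
- A reader might infer that 8.3 mixes one-sided and two-sided levels, taking the 2/510 interval as two-sided. Its upper limit is printed as 0.01. The two-sided value (0.0141) and the one-sided value (0.0123) both round to that, so its sidedness cannot be read. That both exceed 0.01 is a separate matter.
- A reader might infer that the final report will carry the printed bounds, or that the final test will be run one-sided. Nothing says so. The report must use the observed denominator, which 8.3 expects to exceed 553. As an illustration, if 61 women continued, split 30 V1S2 and 31 S1V2 (an assumed split), and all completed, uses would be 30 × 17 + 31 × 13 = 913 and the two-sided limit 1 − 0.025^(1/913) = 0.40%.
- A reader might infer that 4.2.2 requires 0.66% for 0/553. The endpoint in 5.1.1 and the safety population in 8.12 concern devices in this study, and 4.2.2 does not provide for pooling CI01.

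**Conclusion.** The concern holds as a modest error in stated precision. The zero-event limits in 8.3 are not the upper ends of the two-sided exact interval in 4.2.2. By Clopper-Pearson those are 0.72% for 0/510 (printed 0.6%) and 0.66% for 0/553 (printed 0.5%). The 553 statement is too strong on either reading and is supportive evidence only. One-sidedness is inferred from the numbers, since 8.3 does not state it. Pass/fail at zero events with 510 or more rings does not change, and neither the sample size nor the criterion is affected.

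**What to change.** In 8.3, restate the zero-event intervals as (0, 0.0072) for 510 and (0, 0.0066) for 553, and the rates ruled out as 0.72 and 0.66 per 100 devices. Alternatively, keep one-sided limits but label them as one-sided 95%, with 0.54 in place of 0.5 for 553. In either case, mark the 553 figure as supportive. In 4.2.2, name the Clopper-Pearson method and state that 2.5% is placed in the upper tail, including when no events are seen. Make the change before the safety data are analysed.

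The cost is wording in two sections, with the sponsor and IRB approval that section 10 requires for a revision. The downside is that the stated figures become slightly less favourable.

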8.4 Expected Drop-Out Rates

NOTE: The first paragraph below contains out-of-date information, as of this Revision, but is included for reference.

During the pilot investigation (CI01), one participant missed multiple study visits and discontinued the VR101 treatment regimen. However, the participant eventually restarted and successfully completed the investigation, meaning that the drop-out rate for CI01 was 0%. Statistically, if the dropout rate is “0” for a sample size of 21, we can then rule out any drop-out rates higher than 14.6% with 95% confidence (upper bound of the exact Blyth-Still-Casella confidence interval for the proportion 0/21). However, since CI02 requires longer continued participant involvement than CI01, it is possible that the drop-out rate for enrolled participants in CI02 may even exceed 14.6%. We have assumed a 14.6% dropout rate to estimate the number of participants to enroll in the proposed investigation.

The 95% confidence interval used above still underestimated the drop-out rate due to the differing enrollment durations of CI01 and CI02. During the crossover study, which lasted for 11 weeks (per participant), 11 of 72 participants withdrew from the study (1.39% of initial enrollment per week [average], 0.70-2.47% per week [95% CI]. Assuming that half of the participants will participate in the long-term safety study for 9 weeks (Group S1V2) and the remaining half will participate for 13 weeks (Group V1S2), continuation of at least 42 total participants will ensure, with 95% confidence, that 30 participants will complete the long-term safety evaluation (13 consecutive weeks of VR101 use).

Since participants will need to be re-consented when this protocol revision takes effect, the number of additional dropouts (not accounted for by the calculation above) when participants are presented with the new Informed Consent Form is unknown. Therefore, we will offer

J3 Bioscience, Inc.	Clinical Investigation Plan and Protocol CI02	CI02-CIP Rev. 08 Page 55 of 75
	A Pivotal Clinical Investigation to Evaluate the Safety and Efficacy of J3 Bioscience Lubricating Intravaginal Ring VR101 in Relieving Symptoms of Vaginal Dryness	

participation in the long-term safety study to all available participants (up to 61) to ensure that the goal, of 30 participants using VR101 continuously for 13 weeks in the safety portion of the investigation, is met.

8.5 Pass/Fail Criteria of the Clinical Investigation

The clinical investigation will be considered a success if the null hypotheses for the primary efficacy and safety endpoints are rejected as defined in Section 4.2.1 and 4.2.2, respectively. If these two null hypotheses are rejected, reasonable safety and efficacy of VR101 following long-term sequential use will be established and substantial equivalence of VR101 with the predicate Replens devices will be demonstrated. Results of additional hypothesis testing described in Section 4.2.3 will have no effect on the success or failure of the clinical investigation.

8.6 Interim Analysis

No interim analysis will be performed during the comparative efficacy (crossover) study. Data from the comparative efficacy (crossover) study will be locked and available for analysis following completion of the final participant's Visit 6.

8.7 Subgroups of the Study Population for Data Analysis

A subgroup analysis of all primary and claims validation endpoints will be included for the Menopausal Population (see section 8.12), although this subgroup analysis will have no impact on the success or failure of the study.

8.8 Data Handling for Missing Data

Missing data will be imputed for participants in the intent-to-treat (ITT) population (see Section 8.12) who have missing data-points that affect the Primary Efficacy Hypothesis. Subjects who are missing the Day 28 VHI score will have their score imputed using a last observation carried forward approach (LOCF) within each period of the crossover study. (Note: The periods are VR101 treatment period, sham ring treatment period, and washout period.)

If a participant misses either an entire VR101 or sham ring treatment period (i.e. the participant drops out of the study during the 3-week washout period), the patient's Δ VHI score (see Section 4.2.1) will be imputed using a worst-case observation from the remainder of the study population. Specifically, if a participant completes the sham period but misses the entire VR101 study period, the lowest VR101 Δ VHI value will be assigned, and if a participant completes the VR101 study period but misses the entire sham study period, the highest sham Δ VHI value will be assigned.

J3 Bioscience, Inc.	Clinical Investigation Plan and Protocol CI02	CI02-CIP Rev. 08 Page 56 of 75
	A Pivotal Clinical Investigation to Evaluate the Safety and Efficacy of J3 Bioscience Lubricating Intravaginal Ring VR101 in Relieving Symptoms of Vaginal Dryness	

8.9 Exclusion of Data

All data collected and imputed as described in Section 8.8 will be used for the testing of the Primary Efficacy Hypothesis.

8.10 Justification for Washout Period

The exact duration of benefit provided by VR101 following ring removal has not been determined using objective data (VHI scores) collected during CI01. However, in a follow-up call conducted at the end of CI01 (typically 7 days after VR101 removal), participants were asked how long the moisture provided by VR101 persisted following removal of the final VR101. The median response reported by CI01 participants was that the duration of moisture persistence was 3 days after removal of the last VR101 device, with a minimum reported persistence of effect of 2 hours, and a maximum of 7 days (7-day values were censored at 7 days; that is, this 7-day response was the maximum possible duration of effect that could be reported. 3 out of 18 participants who responded to the question on the duration of moisturizing effect after removal of the last VR101 device reported that the effect lasted 7 days). Based on the data reported, we estimate that 99% of the population would stop experiencing benefit from VR101 in 9.85 days or less, using a generalized extreme value distribution model (R 2.3.2; evd package 2.3-2).

We note that the limitations to this approach are that it is possible that the 3 patients reporting a 7-day response actually experienced benefit beyond 7 days; and the data set is small (18 participants). To account for uncertainties introduced by the small sample size and the censoring of data at 7 days, the estimated 9.85-day duration of the moisturizing effect in 99% of the population after use of the last VR101 device can be very conservatively doubled to 19.7 days. We have been even more conservative, setting the washout period to 21 days to minimize any carryover effect of treatment by the sham or VR101 in the first part of the crossover study to the crossover treatment.

8.11 Adjustment for Multiplicity

If both the primary efficacy and safety hypotheses are met, then hypotheses for Claims 1, 2, and 3 will be tested using a hierarchical testing approach in order to control for multiple testing. Claim 1 will be tested first and if the null hypothesis is rejected, then Claim 2 will be tested. If the null hypothesis for Claim 2 is rejected, then Claim 3 will be tested.

8.12 Definition of Study Populations for Analysis

THE FOLLOWING STUDY POPULATIONS HAVE BEEN DEFINED FOR THIS INVESTIGATION:

Intent-to-Treat (ITT) Primary Efficacy Hypothesis Population: All patients who meet inclusion/exclusion criteria and are randomized will be included. Any missing day 0 or day 28 VHI scores will be imputed as defined in section 8.8.

J3 Bioscience, Inc.	Clinical Investigation Plan and Protocol CI02	CI02-CIP Rev. 08 Page 57 of 75
	A Pivotal Clinical Investigation to Evaluate the Safety and Efficacy of J3 Bioscience Lubricating Intravaginal Ring VR101 in Relieving Symptoms of Vaginal Dryness	

Menopausal Population: All members of the ITT population who self-report to being menopausal (have not experienced a menstrual period in the 12-month period prior to the study).

Safety Population: All VR101 devices in all study arms that are successfully inserted and used in accordance with the provided instructions for use will be included as a basis for determination of SADE proportion.

Claim 1 Population: All participants who report a daily vaginal dryness severity following their first VR101 use (Visit 2/5, depending on study arm) and report a weekly average vaginal dryness severity prior to their first VR101 insertion (Visit 1/4, depending on study arm), will be included in the analysis for Claim 1. See section 5.4.5 for relevant survey questions.

Claim 2 Population: All participants in group V1S2 who respond to the appropriate survey question (see section 5.4.6) immediately following their first VR101 insertion (Visit 1) will be included in the analysis for Claim 2.

Claim 3 Population: All daily diary responses recorded regarding VR101 comfort during use (see section 5.4.6) will be included in the analysis for Claim 3.

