5.3.9 Procedures for the Replacement of Participants

As described above, additional participants will be enrolled to account for the maximum expected drop-out rate to ensure that at least 60 participants complete the efficacy portion of the study and at least 30 participants complete the safety portion of the study.

J3 Bioscience, Inc.	Clinical Investigation Plan and Protocol CI02	CI02-CIP Rev. 08 Page 33 of 75
	A Pivotal Clinical Investigation to Evaluate the Safety and Efficacy of J3 Bioscience Lubricating Intravaginal Ring VR101 in Relieving Symptoms of Vaginal Dryness	

The handling of data from participants who do not complete the study is described in Sections 8.8 and 8.9.

VR101 safety data (recording and analyses of adverse events) will be included in the assessment of safety endpoints regardless of how long a participant remains in the study.

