4. Participants will undergo a brief vaginal health assessment which will include a pH test and assignment of VHI scores (see Table 6). During Visit 1, if a participant is assigned a VHI score of 22 or lower (and met all other inclusion/exclusion criteria), she will be enrolled in the study and randomized. The participant will be assigned the next available (lowest remaining) Participant Number.
5. Enrolled participants will be provided with a package of either at least 6 each VR101 devices or at least 6 each sham controls (one for each of the first 4 weeks and at least 2 spares) with printed instructions for use. During Visit 1, the Participant will be given a package containing the Participant Number followed by the letter "A" (for example Participant 1 will be given a package labeled "1A"). During Visit 4, the Participant will be given a package containing the Participant Number followed by the letter "B" (for example Participant 1 will be given a package labeled "1B"). Participant numbers will be pre-randomized by the Sponsor, and only the Sponsor will have access to the randomization schedule. No additional information, verbal or otherwise, will be provided by the clinician to participants on the use of the device.
6. Enrolled participants will be shown to a private clinic area or restroom to self-insert one of the devices from package "A" (Visit 1) or "B" (Visit 4).
7. After insertion, participants will be asked to complete a Post-Insertion Survey that queries their first impressions of the IVR and the insertion process. If a participant has difficulty with placement, she can choose to not place the ring and will be withdrawn from the study. The first ring will remain in the vagina for 7 ± 2 days.
8. Participants will be given a daily diary to complete and return to study staff at each subsequent study visit. The diary will request information on comfort of device use during daily activities and symptoms of vaginal dryness.

J3 Bioscience, Inc.	Clinical Investigation Plan and Protocol CI02	CI02-CIP Rev. 08 Page 39 of 75
	A Pivotal Clinical Investigation to Evaluate the Safety and Efficacy of J3 Bioscience Lubricating Intravaginal Ring VR101 in Relieving Symptoms of Vaginal Dryness	

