Read ALL Instructions before inserting and removing VR101.

1. Wash and dry your hands thoroughly.
2. Remove ring from its pouch.
3. Before inserting VR101, find a position that is comfortable. You can insert the ring while lying down, squatting, or standing with one leg up, whatever position is most comfortable for you.
4. Hold the ring between your thumb and first finger, pressing opposite sides of the ring together. You may want to twist it into a figure 8.
5. It may help you to hold open the folds of skin around your vagina with your opposite hand while inserting the ring.
6. Place the tip of the ring in the vaginal opening and then push the folded ring gently into your vagina. Push the ring up and toward your back. Do not use any lubrication.
7. If you feel any discomfort, the ring probably is not inserted far enough. Try gently pushing the ring further into your vagina. The ring will not get lost in your body.
8. When you are finished, wash and dry your hands thoroughly.

Return any rings that you were unable to place for any reason to the clinic at your next visit.

Before returning a ring to the clinic, place in the original foil-lined pouch if available. If not, place in a zip lock-type bag.

Warnings:

- Do not use the ring if it appears to be damaged and/or if the package appears open or damaged.
- Do not re-insert a ring that you removed or that was expelled if it appears damaged or contaminated. You may wash it in clean water and re-insert it if it is clean. Or, use a new ring. Return any rings you chose not to re-insert to the clinic at your next visit.

VR101 Removal Instructions

Remove each VR101 ring after 7 days of use.

1. Wash and dry your hands.
2. Choose the position that is most comfortable for you.
3. Put your index finger into your vagina and hook it through the ring and gently pull downward and forward to remove the ring.
4. Discard the used ring in the trash and out of reach of children and pets. Do not flush the ring in the toilet.
5. Insert a new ring after removal of the used ring, according to the instructions provided above.

Warning: Do not re-insert a ring that you removed or that was expelled if it appears damaged or contaminated. You may wash it in clean water and re-insert it if it is clean. Or, use a new ring. Return any rings that were unable to be replaced to the clinic during your next visit. Before returning a ring to the clinic, place in the original foil-lined pouch or in a zip lock-type bag.

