13.3 Anticipated Adverse Device Effects (ADE)

Following is a list of adverse events that may be related to the use of VR101 or the sham:

- Device-related discomfort
- Device-related vaginal itching/burning/irritation

J3 Bioscience, Inc.	Clinical Investigation Plan and Protocol CI02	CI02-CIP Rev. 08 Page 62 of 75
	A Pivotal Clinical Investigation to Evaluate the Safety and Efficacy of J3 Bioscience Lubricating Intravaginal Ring VR101 in Relieving Symptoms of Vaginal Dryness	

- Device-related non-menstrual bleeding
- Toxic-shock syndrome
- Ring adherence to the vaginal wall
- Inability of user to remove the ring
- Bowel obstruction
- Ring breakage that causes injury
- Device-related infection
- Device-related vaginal/cervical irritation
- Physical interference with other intravaginal or intrauterine devices

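### The pass/fail SADE proportion has two incompatible definitions, and the narrower one can leave out serious harms from failed insertion, misuse, ring retention or onset after removal

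*Combined protocol and SAP*

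**What the plan says.** Narrow text:

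- Section 8.12 defines the Safety Population, the basis for the SADE proportion, as "All VR101 devices in all study arms that are successfully inserted and used in accordance with the provided instructions for use".
- The hypothesis in 4.2.2 carries the same condition: "VR101, when used in accordance with provided instructions for use will not result in a rate of occurrence".
- The numerator of P(safety) in 4.2.2 is the "Total number of initiated VR101 uses without a participant reporting a serious adverse device effect during VR101 use", which adds a time limit.
- Section 8.3 frames its two-SADE scenario on devices used according to instructions.

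Broad text:

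- That same numerator in 4.2.2 refers to initiated uses, and its denominator is all VR101 devices used.
- Endpoint 5 (5.1.1) relates SADEs to all VR101 devices used in the study, with no condition on instructions or timing.
- Section 5.3.5 says all safety data enter the primary safety test, and removes partial ring uses only from the ring count.
- Section 5.3.9 says VR101 safety data "will be included in the assessment of safety endpoints regardless of how long a participant remains in the study".
- Section 8.3 says rings used for less than 5 days are in the safety sample. This conflicts with the ring count in 5.3.5.

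The pass rule in 4.2.2 is that the "upper bound of the two-sided exact 95% confidence interval surrounding the proportion of SADE occurrence ('P(SADE)') is 0.01 or less". Section 8.5 makes it one of the two conditions for trial success.

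**The concern.** Under 8.12, whether a ring enters the analysis depends on what happens after exposure begins, and the deciding fact can be the harm itself or its cause. The protocol names such cases:

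- **Failed insertion.** Such a ring is not successfully inserted. In 5.4.3, "If a participant has difficulty with placement, she can choose to not place the ring and will be withdrawn from the study".
- **Retention.** Section 13.3 lists "Inability of user to remove the ring" and adherence to the vaginal wall as anticipated device effects. The instructions in 5.6 say "Remove each VR101 ring after 7 days of use", so a ring that cannot be removed falls outside them.
- **Use error.** Placement in the urinary tract and use of a damaged device (13.5) depart from the instructions.
- **Late onset.** Infection or toxic shock (13.3) starting after removal is not during use. With weekly replacement the gap is mainly the V1S2 washout and sham period and the time after the last ring.

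No section says who judges adherence to the instructions, by what rule, or whether this is done before the event is known. The long-term phase is open-label (5.3.4). VR101 is meant to be used unassisted, possibly over the counter (3.7), and failed insertion, retention and misuse are relevant hazards in that setting. A success criterion that can be read two ways lets the choice be made after the events are seen.

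**Working it through.** **Inputs.** Planned exposure (8.3): 30 × 13 + 30 × 4 = 390 + 120 = 510 VR101 rings in CI02; adding 43 from the pilot CI01 gives 553. Pass rule (4.2.2): two-sided exact 95% upper bound ≤ 0.01.

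**Formula.** For x SADEs in n rings, the Clopper-Pearson upper bound is the 0.975 quantile of Beta(x + 1, n − x). The one-sided 95% version uses the 0.95 quantile.

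**The plan's own figures (8.3).**

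- 2/510, stated (0.00, 0.01): two-sided gives (0.0005, 0.0141). This matches only because it is printed to two decimals. Unrounded, 1.41% fails the 1% rule.
- 0/510, stated upper bound 0.006: two-sided 0.0072, one-sided 0.0059. The stated value matches the one-sided bound.
- 0/553, stated upper bound 0.005: two-sided 0.0067, one-sided 0.0054. Again one-sided.

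The printed intervals therefore understate how tight the two-sided rule is.

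**What one uncounted SADE does.**

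| Exposure | SADEs counted | Upper bound | Result |
|---|---|---|---|
| 510 (8.3) | 0 | 0.72% | pass |
| 510 | 1 | 1.09% | fail |
| 510 | 2 | 1.41% | fail |
| 553 (with CI01) | 1 | 1.003% | fail |
| 900 (assumed) | 3 | 0.97% | pass |
| 900 | 4 | 1.13% | fail |

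The 900 assumes that all 60 completers finish the long-term phase under Rev. 08: 30 V1S2 women × (4 + 13) + 30 S1V2 women × 13 = 510 + 390. The smallest ring counts that pass are 368 with 0 SADEs, 555 with 1, 720 with 2 and 874 with 3.

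**Effect on the error rate (illustrative).** The documents give no figure for the share s of SADEs that would be counted, so a range is shown. If the true rate over all uses is 1%, only zero counted SADEs pass at 510 rings, and the chance of passing is (1 − 0.01s)^510:

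- s = 1: 0.6%
- s = 0.8: 1.7%
- s = 0.5: 7.8%
- s = 0.25: 27.9%

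**Direction of the fix.** Counting all initiated uses can add events, but it also adds event-free rings. One SADE in 540 rings gives 1.03% (fail). Adding 20 event-free rings gives 1/560 = 0.99% (pass).

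**The case against.** The strongest reply is that the plan already counts everything. Section 5.3.5 speaks directly to the primary safety test and puts all safety data in, and Endpoint 5 and 5.3.9 agree. On that view 8.12 limits only the ring count while every SADE stays in the numerator, which would push the proportion up. This stands as a possible reading. A reader might infer from 8.12 that these SADEs are definitely dropped, and the documents do not support that. They equally do not rule it out: 8.12 is the formal definition of the set, and the hypothesis in 4.2.2 carries the same condition.

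A reader might also infer that rings worn 8 or 9 days are excluded, since the instructions say 7 days and 5.4.3 allows 7 ± 2. No section says so; the passages disagree and must be reconciled. Nor does withdrawal after a failed placement mean that the woman's events are discarded, given 5.3.9.

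On size, one event decides any exact-bound rule at its boundary, and Rev. 08 sends all participants into long-term use, so exposure may well exceed 510. Both points are fair, and they limit the impact to the boundary count. At 510 rings, however, that boundary is the first SADE.

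Finally, the device logs (12.5) record rings issued and returned, not insertion attempts, and used rings are thrown away. A denominator of every attempted insertion may not be fully recoverable.

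**Conclusion.** The concern holds as an unresolved contradiction in both numerator and denominator of a success criterion, with one reading that can leave out serious device-related harms and bias the SADE proportion downward. It does not hold as a settled exclusion.

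At the planned 510 rings, a single SADE left uncounted turns a fail (1.09%) into a pass (0.72%). At an assumed 900 rings the counting rule decides the result only between 3 and 4 SADEs. The sizes rest on the two-sided exact rule in 4.2.2 and on the stated exposures. How many SADEs would fall into the disputed categories is unknown; none was seen with the 43 pilot rings (8.3).

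It would be wrong to expect that a broader count can only worsen the result. It may move either way, because the denominator grows too. The reason to change is that the rule should be fixed before the events are known.

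**What to change.** - **8.12:** define one primary safety set as all initiated VR101 uses, including attempted insertions where recorded, whatever the success of insertion or adherence to the instructions. State the source for the ring count (diaries, visit records, accountability log).
- **4.2.2:** remove the instructions-for-use condition from the primary hypothesis. Replace the during-use limit with every VR101-related SADE from the first insertion attempt through the post-removal follow-up. Say which ring an event after removal is assigned to, for example the last VR101 ring inserted or attempted.
- **5.3.5 and 8.3:** use the same numerator and denominator, and state once whether partial uses count as rings. Under this fix, as initiated uses, they do.
- **Supportive analysis:** keep the per-instructions set, with adherence judged by a written rule and without knowledge of the event.
- **Wear time:** reconcile the 7 days in the instructions with the 7 ± 2 days in the protocol, so that a ring worn within the protocol's own window is not classed as off-instruction in the analysis.

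The cost is small wording changes in four sections. Adverse events are already recorded on a form, and a contact one week after the last ring is planned (5.4.9), so the numerator needs little or no new collection. The denominator is limited to attempts that the trial records.
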